# 5.4 Potential Risks to Subject Confidentiality

In all clinical studies, confidentiality of protected health information may be breached due to study-related activities beyond those of routine clinical care. This risk will be minimized by not collecting personally identifying information on data collection forms or other study related documentation to be provided to the study Sponsor.

#### 6.0 SAFETY MONITORING

[name] will oversee the single center clinical trial as the DMC. A Consulting Statistician may be consulted, if necessary. The DMC will review study progress and study conduct and will be responsible for the decision to stop recruitment or modify the study design, as necessary, throughout the course of the study. Refer to **Section 7.3** for Safety Related Stopping Rules.

#### 7.0 STATISTICAL ANALYSIS PLAN

This is a feasibility study without a primary study hypothesis or statistical comparison.

#### 7.1 Continuous Outcomes

Continuous outcomes will be summarized with mean, standard deviation and other relevant statistically summaries. When not normally distributed, medians and quartiles will be reported. A confidence interval approach may be used, if appropriate, to compare outcomes with historical data.

### 7.2 Binary Outcomes

Binary and ordinal outcomes will be tabulated. Confidence intervals for proportions will be calculated using the exact binomial distribution. A confidence interval approach will be used to compare outcomes with historical data.

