The international single arm CbFAS trial conducted under the original protocol for this study has been completed and the manuscript submitted to Endoscopy journal for publication. See more detail on the preliminary results in separate attachment submitted. In this multicenter, prospective non-randomized trial 39 patients were treated, each subject receiving 1-2 ablations of 6, 8 or 10 seconds. Symptoms were assessed directly and 2 days post-cryoablation. Follow-up endoscopy was performed after 6-8 weeks to assess the ablation response. Outcome parameters were incidence of adverse events, pain, esophageal stricture formation, and ablation response by cryogen dose. *Results*: 56 ablations (10 with 6-sec, 28 with 8-sec, 18 with 10-sec) were performed. Six ablations failed due to device malfunction (n=3) or other reasons (n=3). Median (IQR) procedure time was 7 min (4-10) min. No major adverse events occurred; six patients had a minor mucosal laceration requiring no intervention. Mild pain was reported in 27% of patients immediately after cryoablation and in 14% after 2 days. After 6-8 weeks no strictures had developed. Full squamous regeneration was seen in 6 [60%] of 6s-areas; 23 [82%] of 8s-areas, 100% of 10s-areas). These study results suggest that focal cryoablation of BE with the newly developed CbFAS is feasible, safe, and results in squamous regeneration in the majority of patients. These results were recently published (Scholvinck et al, Endoscopy July 2015 – paper uploaded into eIRB separately)

Furthermore, [name] has treated 41 BE patients and 10 patients with esophageal squamous low grade and high grade dysplasia (neoplasia) within this study and more treated within the clinical cryotherapy program at Johns Hopkins Hospital) with successful ablation in 1-3 outpatient procedures using multifocal cryoballoon ablations, in keeping with standard of care treatment approach to ablation. Research and clinical patients have tolerated cryoablation well, with visible treatment response.

Based upon the results of 2 clinical trials completed under this IRB-approved study,

[name] plans to continue this single center (industry sponsored) study to continue the evaluation of safety, effectiveness and 5-year durability of cryoballoon ablation for esophageal neoplasia.

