**Indications for Use:** 

**Study Purpose:** 

Under this protocol, Cryoballoon ablation will be performed on patients with Barrett's Esophagus (BE) and localized esophageal squamous neoplasia.

Patient Population:

Patients who have Barrett's Esophagus and esophageal squamous neoplasia

and meet the protocol entry criteria.

The purpose of this study is to assess the safety, feasibility and performance

of the C2 Focal Cryoablation System in patients with BE and esophageal

squamous neoplasia.

This study is:

Study Design: • Prospective

Single center (Johns Hopkins Hospital)

Non-randomized

Sample Size: It is estimated that up to 100 patients will be enrolled under this protocol.

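### Does the plan contradict itself by disclaiming a statistical comparison in Section 7.0 and then comparing outcomes with unnamed historical data in Section 7.2?

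*Combined protocol and SAP*

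**What the plan says.** Section 7.0 opens the statistical plan with: "This is a feasibility study without a primary study hypothesis or statistical comparison".

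Section 7.1, on continuous outcomes, makes a historical comparison optional: "A confidence interval approach may be used, if appropriate, to compare outcomes with historical data". Section 7.2, on binary outcomes, states it without condition: "A confidence interval approach will be used to compare outcomes with historical data". Just before that sentence, Section 7.2 specifies exact binomial intervals for proportions. It gives no confidence level, no interval for a difference, and no historical source.

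Preliminary Experience and Data, in the same version, reports that the investigator "has treated 41 BE patients and 10 patients with esophageal squamous low grade and high grade dysplasia (neoplasia) within this study". It explains continuation of the study as "Based upon the results of 2 clinical trials completed under this IRB-approved study". On the predecessor it says: "The international single arm CbFAS trial conducted under the original protocol for this study has been completed". That trial's efficacy is summarised as: "Full squamous regeneration was seen in 6 [60%] of 6s-areas; 23 [82%] of 8s-areas, 100% of 10s-areas".

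The CIP Summary (Section 3.1) gives the size of the study: "It is estimated that up to 100 patients will be enrolled under this protocol".

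**The concern.** Three features together look troubling.

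- **Wording.** One section disclaims a comparison and another commits to one. The two complete-elimination endpoints in Section 3.1 are binary, so Section 7.2 appears to bind exactly where it matters most.
- **Missing comparator.** The documents name no source, rate, endpoint or time point for the historical side. Section 3.2 states a goal of at least 90% ablation of BE and 100% of dysplastic areas, but does not call it historical data.
- **Timing.** If the 51 treated patients count toward the 100, about half the study was treated before a comparator was fixed. Someone who already knows how the results look could choose a flattering one.

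At stake would be the description of the efficacy results as better or worse than past experience. There is also a technical hazard. Section 7.2 names only a one-sample exact interval. Setting that interval against a historical estimate as though it were a known constant ignores the historical sampling error.

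**Working it through.** The plan derives no figure for this comparison, and the 100 has no stated basis, so there is nothing of the plan's own to reproduce. The checks below cover the wording, the timing, and how much the comparator and interval could matter. A two-sided 95% level is assumed throughout, because the plan states none.

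**1. Wording.** In Section 7.0 the adjective "primary" can govern both nouns, so that the sentence excludes a primary hypothesis and a primary comparison. Section 7.2 would then be a secondary, descriptive comparison. On the stricter reading the two sections do conflict. Neither section attaches a null value, margin, alpha or success criterion to the comparison.

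**2. Timing.** 41 + 10 = 51, and 51/100 = 51%, if these patients count toward the 100; the documents do not say. The text gives no response rate for them, only that ablation succeeded in one to three procedures, and its next sentence pools research and clinical patients. Section 3.5.5 places the endpoint analyses at months 12, 24, 36, 48 and 60, and Table 2 puts the biopsy endpoint assessment at 12 months. Nothing says how many of the 51 had reached month 12. So 51% treated is supported; 51% with known endpoint results is not.

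**3. Spread of the available historical rates.** Inputs from Preliminary Experience and Data are 10, 28 and 18 ablations at 6, 8 and 10 seconds. The counts agree with the percentages: 6/10 = 60%, 23/28 = 82.1%, 18/18 = 100%. Clopper-Pearson intervals are 26.2-87.8%, 63.1-93.9% and 81.5-100%.

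With assumed current results x/100, the difference is x/100 − y/m with a Newcombe interval, in percentage points:

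| Assumed result | vs 6/10 | vs 23/28 | vs 18/18 |
|---|---|---|---|
| 80/100 | +20.0 (−4.8 to 49.5) | −2.1 (−15.5 to 16.8) | −20.0 (−28.9 to −1.2) |
| 85/100 | +25.0 (0.4 to 54.3) | +2.9 (−10.1 to 21.5) | −15.0 (−23.3 to 3.5) |
| 90/100 | +30.0 (5.7 to 59.1) | +7.9 (−4.6 to 26.1) | −10.0 (−17.4 to 8.1) |

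The sign does change with the comparator. But these are regeneration rates per treated area, by dose, at 6-8 weeks. The study endpoint is complete elimination in a patient who may have up to five sessions. The table shows the spread available, not a comparison the plan calls for.

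**4. Treating a historical estimate as fixed.** Let X ~ Bin(100, p) be the current result and Y ~ Bin(m, p) the historical one, with equal true rates p = 0.80, 0.85 and 0.90. The probability that the exact interval for X/100 excludes Y/m, by full enumeration, is:

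- m = 39 (the predecessor's patient count): 27.0%, 27.5%, 28.8%
- m = 100 (assumed): 14.6%, 14.3%, 14.1%
- m = 400 (assumed): 6.2%, 6.1%, 5.7%
- benchmark fixed in advance: 3.3%, 3.4%, 4.4%

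Over the same three historical sizes, a Newcombe interval for the difference excludes zero in 4.3-5.0% of studies. The inflation comes entirely from a procedure that Section 7.2 does not prescribe. The m = 39 case is also hypothetical, since the predecessor's efficacy is reported per area and no rate out of 39 patients is given.

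**5. Denominators.** Squamous patients do not belong in a BE-elimination rate, and BE patients may enter with or without dysplasia (Section 3.4). The denominator of either efficacy endpoint is therefore not known to be 100, and the figures in steps 3 and 4 are illustrations only.

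**The case for a change.** The strongest case for a change is that the plan itself makes the commitment. Calling the study a feasibility study does not excuse an unconditional comparison with nothing named on the other side. The present version was written with more than half the maximum enrolment already treated and favourably described. If those 51 do not count toward the 100, they become the nearest historical data, and a sentence would be needed to say so. The exact interval stands directly before the comparison sentence, so using it against a historical estimate is a natural misreading. The remedy is also cheap: delete one sentence, or name a source.

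Part of this stands. The sections are loosely worded, the comparator is unwritten, and the status of the 51 is not stated. A reader should not treat any historical comparison from this study as prespecified. But cheapness does not show that a stated rule is wrong. A two-sample interval and separate reporting of earlier and later patients would be reasonable choices. They are preferences within a descriptive analysis, and splitting has a price: with an assumed 90% response, 44/49 has an exact interval of 77.8-96.6% (18.8 points wide) against 82.4-95.1% (12.7 points) for 90/100. Nor would any interval or chosen source remove differences in case mix, dose, number of sessions or prior resection, which are the main limit on such a comparison.

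**Conclusion.** No change is needed. The inconsistency is one of loose wording, and the missing comparator is a gap in a descriptive, single-arm feasibility study. A competent analyst fills it by tabulating the endpoints with the exact intervals already specified and by citing the source of any historical figure. The analyst would also match its endpoint and time point, allow for its sampling error if it is an estimate, and call the comparison descriptive.

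The size of the issue is limited to presentation. The choice of comparator can reverse the sign of a reported difference (+25.0 against −15.0 points for an assumed 85/100), but only with rates that do not match the endpoint. The 27-29% exclusion rate against a 39-patient source arises only under a method the plan does not set out. No sample size, stopping rule or success criterion turns on either.

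This conclusion rests on reading Section 7.0 as excluding a primary or formal comparison, and on the absence of any decision rule. The true rates, current results, 95% level and historical sizes of 100 and 400 are assumptions. If a performance claim were later hung on the historical comparison, the missing comparator would become a real defect.

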### 7.3 Safety Related Stopping Rules

The principal investigator will be charged with monitoring the study for safety and for auditing the quality of the data. If there are any perceived safety concerns related to the system or therapy, a corrective action may be implemented or the trial may be terminated.

The principal investigator will meet periodically during the study, after every 10 patients are enrolled and treated, to review any safety concerns. After 20 patients are enrolled and treatments are completed, the DMC will meet to review preliminary efficacy data

Should any of the following occur within 30 days following treatment and be, in the opinion of the investigator, directly attributable to the Therapy or System, the DMC will be alerted as soon as feasible (not to exceed 48 hours of knowledge of the event) and study treatments will be suspended without delay.

- Death or an incident leading to death
- 5 consecutive patients with device malfunctions
- 5 consecutive patients with moderate or severe stenosis in treatment area.

The DMC will review the details surrounding the above-listed event(s) and will be charged with making one of the following decisions:

- Continue without modification to the study protocol or conduct
- Continue with modification

C2 Therapeutics, Inc.

Stop the study

Should the study continue, but with modification (to the System or the study documentation) or if the decision is made to stop the study, the reviewing Ethics Committee(s) and where applicable, the governing agency(ies), will be alerted. Treatments will not commence until the necessary EC approvals for the modification have been obtained.

NOTE: If the decision is made to stop the study, treatments and patient screening activities will cease, however, patient follow up will continue as planned.

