### Complications:

- Allergic reaction to the medications given
- Cardiac arrhythmia (irregular heartbeats which could be life-threatening)
- Inhalation of gastric secretions (breathing in of fluid in the stomach)
- Infection
- Hemoptysis (coughing up of blood)
- Over-sedation requiring sedation reversal
- Perforation or laceration (small hole or tear) of the esophagus
- Decreased respiration
- Stricture (narrowing of the esophagus)
- \*Ingestion of the fluid in the cryoballoon which may result in discomfort/stomach bloating
- Death

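### Apart from an unbroken run of five investigator-attributed stenoses within 30 days, no non-fatal serious harm has a set route to the DMC

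*Combined protocol and SAP*

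**What the plan says.** Section 6.0 appoints one person, whose name is removed, as the DMC. That person reviews progress and conduct and "will be responsible for the decision to stop recruitment or modify the study design, as necessary, throughout the course of the study". The section sets no meeting schedule and names no safety data to be supplied.

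Section 7.3 gives the detail:

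- **Dated DMC meeting.** There is one, and its subject is efficacy: "After 20 patients are enrolled and treatments are completed, the DMC will meet to review preliminary efficacy data".
- **Periodic safety review.** This is the principal investigator's: "The principal investigator will meet periodically during the study, after every 10 patients are enrolled and treated, to review any safety concerns". No step passes the result to the DMC.
- **Event alerts.** The DMC is told within 48 hours, and treatments are suspended, for three events: a death or an incident leading to one, device malfunction in five patients in a row, or moderate or severe stenosis in five patients in a row. Each must fall within 30 days of treatment and be, "in the opinion of the investigator, directly attributable to the Therapy or System".

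Section 8.7.3 sends SAE reports to the sponsor and the IRB/EC. Section 8.6 lets the investigator or the sponsor stop the study. Neither names the DMC.

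On numbers, section 3.1 states: "It is estimated that up to 100 patients will be enrolled under this protocol". Under Preliminary Experience and Data, the protocol reports that one clinician "has treated 41 BE patients and 10 patients with esophageal squamous low grade and high grade dysplasia (neoplasia) within this study".

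**The concern.** The body that decides on stopping should see the data on which that decision depends. Read literally, the plan gives the DMC an efficacy look and three narrow alerts, while the regular safety review and the serious-event reports go elsewhere. The investigator's own view of causation decides whether even an alert event is passed on.

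Adverse events are among the primary endpoints in section 3.1. Exposure per patient is also far higher than in the completed 39-patient trial: 1 to 2 ablations there, against up to 24 per session over up to 5 sessions here. If an esophageal perforation occurred, the plan could be followed to the letter without the DMC hearing of it.

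**Working it through.** The plan has no hypothesis, power or stopping probability to reproduce (section 7.0). The check has three parts.

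**1. Which events have a stated route to the DMC**

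| Event | Route stated elsewhere | Route to the DMC |
|---|---|---|
| Death within 30 days, judged attributable | SAE report (8.7.3) | 48-hour alert (7.3) |
| Death within 30 days, attributed to something else | SAE report | None stated |
| Five consecutive patients with malfunction | None checked | 48-hour alert, if attributed |
| Five consecutive moderate or severe stenoses within 30 days | AE record (4.0, 5.2) | 48-hour alert, if attributed |
| Isolated or non-consecutive severe stenosis | AE record | None stated |
| "Perforation or laceration (small hole or tear) of the esophagus" | Always an AE (5.2); SAE report if serious | None stated, unless it leads to death |
| SADE or UADE (defined in 9.0) | SAE report where it meets the SAE definition; the sponsor may stop for a UADE (8.6) | None stated |

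The run of stenoses is the only non-fatal harm with a set route.

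**2. Whether the stenosis alert can operate**

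*Timing.* The window is 30 days. Stenosis is graded by its shape and by whether an endoscope passes, so grading needs an endoscopy. Section 3.5.4 and Table 2 place the follow-up endoscopy at 8 to 12 weeks, which is 8 × 7 = 56 to 12 × 7 = 84 days. One sentence in section 3.2 says 6 to 12 weeks, and even 6 × 7 = 42 days is outside the window. Between discharge and day 30, Table 2 lists only phone contacts. A graded stenosis inside the window would need an unscheduled endoscopy, in five consecutive patients.

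*Run length.* Now set timing aside and suppose that every stenosis is seen and attributed. The documents give no stenosis rate for this level of exposure, so the rate p is assumed and varied. Patients are treated as independent. Following the current run length (0 to 4) from patient to patient gives the exact chance of at least one run of five. The chance of five or more cases in any order is the binomial tail.

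| Assumed p | Run of 5 in 49 patients | Run of 5 in 100 patients | 5 or more cases in 49, any order |
|---|---|---|---|
| 10% | 0.04% | 0.09% | 55% |
| 20% | 1.2% | 2.4% | 98% |
| 30% | 7.5% | 15% | over 99.9% |
| 50% | 54% | 81% | about 100% |

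Hand check at p = 0.20 and n = 49: the chance is at most p⁵ × [1 + (n − 5)(1 − p)] = 0.00032 × (1 + 44 × 0.8) = 0.00032 × 36.2 = 0.0116. The exact value is 0.0115.

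**3. Where the dated meeting falls**

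- Treated within the study: 41 + 10 = 51.
- Past the 20-patient mark: 51 − 20 = 31.
- Remaining, if the 51 count toward 100: 100 − 51 = 49.

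On that reading, the principal investigator's reviews continue at 60, 70, 80, 90 and 100, and the DMC has no dated meeting left. If the count restarts, one DMC meeting remains, on efficacy. On neither reading is there a dated DMC safety review.

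**The case against.** The strongest reply is that the DMC may already see everything. Section 6.0 names one person as the DMC and section 8.0 names the principal investigator; both names are removed. If they are the same person, the DMC conducts the 10-patient reviews and learns of every event. Forwarding tables would then change nothing, and the weakness would be lack of independence. This stands as a limit, because the documents cannot settle it.

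Second, serious events do not vanish. SAEs go to the sponsor and IRB/EC, the principal investigator may act on any perceived safety concern, the sponsor may stop at once for a UADE, and the DMC has a standing remit. This is true and lowers the stakes. But that remit comes with no data feed, and the other routes do not inform the body given the stopping decision. The reporting details in section 8.7.3 may have been lost from the text available, so their absence is not counted.

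Third, this is a single-center feasibility study of an FDA-cleared device, and the protocol reports that the patients already treated tolerated multifocal ablation well. That argues for light oversight, which the remedy respects.

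Three stronger readings are tempting and unsupported:

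- A reader might infer that no non-fatal harm can reach the DMC. The stenosis run is a set route, even if nearly closed.
- A reader might infer that the 20-patient meeting lapsed or was missed. That meeting also requires completed treatments, which the protocol does not report for the 51, and it may have been held.
- A reader might cite the lacerations in 6 of the 39 earlier patients as serious harm without a trigger. The protocol calls them minor, says they needed no intervention, and reports no major adverse events.

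**Conclusion.** The point holds in limited form. Of the non-fatal serious harms, only a run of five attributed stenoses within 30 days has a set route to the DMC, and scheduled endoscopy does not fall in that window. Perforation, SADE, UADE and isolated severe stenosis have no stated route. Nor does a 30-day death that the investigator attributes elsewhere, unless another trigger applies.

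This follows from the wording of section 7.3 read with sections 6.0 and 8.7.3, and does not depend on how the 51 patients are counted. Two things are conditional: the figure of up to 49 further patients with no dated DMC meeting requires that the 51 count toward the 100, and the run probabilities rest on assumed rates and independence between patients. It also assumes that the DMC and the principal investigator are different people; if not, the finding becomes one of independence. The sponsor should make the change, since it is cheap and the gap concerns a primary endpoint.

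**What to change.** In section 7.3:

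1. Send the existing every-10-patient safety review to the DMC for the rest of enrollment.
2. Extend the existing 48-hour DMC alert to every SADE, every UADE, every esophageal perforation, and every death within 30 days whatever the investigator's attribution. These additions are notifications only; any suspension is left to the DMC.
3. Reconcile the 30-day window of the stenosis trigger with the 8 to 12 week endoscopy at which stenosis is assessed.

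The sponsor should also state whether the 51 patients count toward the 20 and the 100, whether the 20-patient meeting was held, and whether the person acting as the DMC is the principal investigator. If so, the independence of the review needs to be addressed, since items 1 and 2 alone would add little.

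The cost is protocol wording, forwarding reviews that are already held, and a few extra DMC communications. No new procedure or visit is needed for items 1 and 2.

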**CONFIDENTIAL** 

<sup>3 Stricture formation is defined as none, mild (non-circumferential stenosis allowing easy passage of diagnostic endoscope), moderate (circular stenosis allowing passage of diagnostic endoscope), and severe (any stenosis preventing the passage of a diagnostic scope).

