#### 3.5.3 Stage 3) Patient Follow-up

The follow-up period begins immediately post-procedure. The patient will undergo a follow-up assessment immediately post-procedure / prior to discharge. The patient will undergo a safety phone contact at 1 days (±1 days), 8 (±1 days) days, and 1 month post treatment. Assessment of pain score (0-10 Likert scale), dysphagia score (0-4), odynophagia, diet, medications (including narcotic analgesics) will be performed using a standardized questionnaire.

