#### Table 2 - Schedule of Treatments and Assessments

\*Adverse events occurring prior to the procedure will be documented in the patient's medical record but will not count as related to the investigational device or procedure.

\*Treatments: Baseline or initial treatment visit = visit 0; subsequent treatments: 2nd to 5th treatment visits (10 weeks), as needed, up to 12 months from baseline. Treatments only if there is visible residual disease; no endoscopically- visible BE or abnormal squamous mucosa, biopsy will be performed using standardized protocol, beginning at the gastric cardia then the neo-Z line and every 1-2 cm proximal, to sample the previously treated BE areas (according to current standard of care).

Subjects can opt-out of participating in the surveillance phase of the trial after 12 months, if local endoscopic surveillance is preferred.

Adverse events: any patient with pain, dysphagia, fever, or other non-serious adverse event will be called weekly from day 8 to 1 month post-treatment or until AE resolution. Adverse events will be graded and recorded according to standard NIH definitions.

STUDY STAGES $\rightarrow$	Stage 1	Stage 2		Stage 3		Stage 4	Stage 5	Stage 6	
Assessments	Informed Consent/ Baseline Evaluation	Initial Treatment *	Immediately Post-/prior to discharge (up to 12 hours)	1-day Phone Contact (±1 day)	7-day Phone Contact (+/- 1 day)	30-day Phone Contact (+/- 1 day	EGD for treatment or biopsy ( q 8-12 weeks)	EGD for biopsy (endpoint assessment) (12 months)	EGD (24, 36, 48 and 60 months)
Consent	X								
Review of Medical History	x								
Review of Medications	Х	Х	X	Х	Х	Х	X		
Review of General Health	x	х	X	Х	X	X	x		
Physical Exam	X								
Pain and dysphagia Assessment		х	X	X	X	X	x	X	

PROTOCOL# CP-0007/ Version: 8 29April 2019

CONFIDENTIAL

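### The stenosis suspension trigger in section 7.3 closes at day 30, but the endoscopy needed to grade stenosis is first scheduled 26 to 54 days later

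*Combined protocol and SAP*

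**What the plan says.** Section 7.3 lists three events that suspend study treatments and require an alert to the DMC within 48 hours of knowledge: a death, five consecutive patients with device malfunctions, and "5 consecutive patients with moderate or severe stenosis in treatment area". All three share one window, "Should any of the following occur within 30 days following treatment", and one attribution condition, "in the opinion of the investigator, directly attributable to the Therapy or System". Section 7.3 also has the principal investigator meet "after every 10 patients are enrolled and treated, to review any safety concerns".

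The stricture footnote (section 3.1, repeated at 3.5.4) defines the grades endoscopically. Moderate is a circular narrowing that a diagnostic endoscope can still pass; the top grade is "severe (any stenosis preventing the passage of a diagnostic scope").

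After the pre-discharge check, section 3.5.3 schedules telephone contacts only: "The patient will undergo a safety phone contact at 1 days", then at about one week and at 1 month, with pain and dysphagia scores. Stenosis is evaluated at the Stage 4 endoscopy, which section 3.5.4 places at 8 to 12 weeks. Table 2 agrees: "EGD for treatment or biopsy ( q 8-12 weeks"). A note to Table 2 adds that patients with symptoms "will be called weekly from day 8 to 1 month post-treatment or until AE resolution".

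**The concern.** Two of the three triggers fit a 30-day window: a death or a malfunction is known when it happens. Stenosis is different, because its grade depends on an endoscopic examination and none is scheduled inside the window. The trigger therefore does not refer to the visit that supplies its data.

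At stake is a safety rule, not an estimate. Stricture formation is a listed endpoint. The only human stricture result in the protocol (Preliminary Experience and Data) is that none had developed after 6 to 8 weeks in the 39-patient trial. Those patients had 1 to 2 ablations each, whereas this protocol allows up to 24 per session and up to 5 sessions. The earlier result may not carry over, so the trigger should be able to use what the Stage 4 endoscopy finds.

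**Working it through.** The plan gives no operating characteristic for this rule, so there is no stated figure to reproduce.

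**Step 1: the gap in days.** Weeks × 7, minus 30:

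| Source of the endoscopy time | Days after treatment | Days after the window closes |
|---|---|---|
| 3.5.4, Table 2 and the list in 3.2: 8–12 weeks | 56–84 | 26–54 |
| Note to Table 2, repeat treatments: 10 weeks | 70 | 40 |
| One sentence in 3.2: 6–12 weeks | 42–84 | 12–54 |

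The gap is positive under every wording. The operative schedule gives 26 to 54 days; the 12-day figure rests on one phrase in 3.2.

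**Step 2: the two readings of *occur*.**

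- *Detection.* A stenosis first seen at Stage 4 is outside the window and does not count.
- *Onset.* This is the likelier reading, because 7.3 separately starts the 48-hour clock at knowledge of the event. Stricture is always reported as an AE (5.2), and every AE gets an onset date from the investigator (4.0). With dysphagia in the first month, that date has evidence behind it. Without symptoms, an endoscopy at day 56 to 84 shows that a stenosis exists but not when it formed, so the date is a judgement.

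**Step 3: how much the window matters.** Let p be the rate of attributable moderate or severe stenosis per patient, and f the share of cases dated within 30 days. The documents give neither, so both are assumptions, as is independence between patients. Each patient counts with probability q = f × p.

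Let s_j (j = 0 to 4) be the probability that the current run has length j and no run of five has yet occurred. Start with s_0 = 1. For each patient, new s_0 = (1 − q) × Σ s_j, new s_(j+1) = q × s_j, and q × s_4 is added to the trigger probability.

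| Assumed p | f = 1, n = 100 | f = 0.5, n = 100 | f = 0 | f = 1, n = 49 |
|---|---|---|---|---|
| 10% | 0.09% | 0.003% | 0 | 0.04% |
| 20% | 2.4% | 0.09% | 0 | 1.2% |
| 30% | 15.3% | 0.62% | 0 | 7.5% |

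Hand check for f = 1, n = 100: the expected number of runs reaching five is q⁵ × [1 + 95 × (1 − q)], an upper bound on the probability. It gives 0.00001 × 86.5 = 0.09% at 10%, 0.00032 × 77 = 2.5% at 20% and 0.00243 × 67.5 = 16.4% at 30%, consistent with the table.

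The column n = 49 applies if the 41 Barrett's and 10 squamous patients already treated count toward the 100 (100 − 41 − 10 = 49).

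The most that correcting the window can add is the move from f = 0 to f = 1: 0.09, 2.4 and 15.3 percentage points. From f = 0.5 the additions are 0.08, 2.35 and 14.6 points.

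**Step 4: a reference rate.** If all 39 patients in the earlier trial were assessed, 0 of 39 gives an exact two-sided 95% upper limit of 1 − 0.025^(1/39) = 9.0%. At that rate, with every case counted, the trigger has a 0.05% chance of firing in 100 patients.

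**The case against.** The strongest reply is that this is an ambiguity and not a contradiction, and that little turns on it. On the onset reading, late detection does not exclude a case. Dysphagia is scored by questionnaire through 1 month and symptomatic patients are called weekly, so many onsets can be dated. Other provisions reach a week-8 stenosis without any 30-day limit: the review after every 10 patients, SAE reports to the sponsor (8.7.3), action on any perceived concern (7.3), and discontinuation for unexpected incidence of a known AE (8.6). At rates of 10 to 20%, five in a row is rare even with every case counted. This is also a feasibility study with no hypothesis.

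Most of that stands, and it limits the point. It does not remove it. Symptom records cannot date a stenosis that caused no symptoms, and a moderate stenosis by definition still lets the endoscope through. The documents do not say how common silent cases are. The other provisions permit action; only the listed triggers require suspension.

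A reader might infer that the trigger can never fire, or that strictures go unmonitored. The documents support neither. Symptoms could lead to an unscheduled endoscopy before day 30, an onset can be dated within the window, and the 10-patient review is required, although the response to it is discretionary.

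**Conclusion.** The point holds as a weakness in one safety rule. Its stenosis limb is not tied to the visit where stenosis is graded, 26 to 54 days after the window closes (12 days at the least, on the single 6-week wording). Whether a stenosis first found at that visit counts depends on the reading of *occur*, or on a back-dated onset.

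The size is modest: at most 0.09, 2.4 and 15.3 percentage points at assumed rates of 10%, 20% and 30%. These figures assume 100 independent patients and compare counting none of the cases with counting all of them. Nothing in the documents supports a rate as high as 30%. No estimate or analysis changes.

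A reader might also infer that a corrected window would make the rule sensitive. It would not at 10 to 20%, because there the five-in-a-row threshold is the limit. The case for the change is that it is specific and nearly free.

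**What to change.** In section 7.3, keep 30 days for death and device malfunction. For stenosis, write:

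> Attributable moderate or severe stenosis in the treatment area found at any endoscopy up to and including the first follow-up endoscopy after a treatment session, whenever that visit takes place and whatever the onset date.

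For the run of five, add:

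- Patients are ordered by first treatment.
- Each is classified by the first follow-up endoscopy after the first session, or by an earlier unscheduled endoscopy that shows stenosis.
- Patients not yet examined neither complete nor break a run.
- Moderate or severe stenosis after a later session goes to the DMC for review.

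The attribution condition and the 48-hour alert stay as they are. The wording sets no cap in weeks, so a stenosis found at a late visit still counts.

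The cost is text in 7.3 only, with no added visits or data. There are two downsides: the trigger may fire somewhat more often, and recently treated patients stay unclassified until their endoscopy while treatment of others continues. The five-in-a-row threshold is a separate choice, left unchanged here.
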